### 7.2.4 Smoking Cue Appeal Questionnaire

The Smoking Cue Appeal Questionnaire will be presented as frequency table of the scores for each question included in the questionnaire. Each table will compare, for each visit in which the questionnaire was administered, the Hnb group and the EC group frequency of answers (Table E.4b1).

The t-test will be carried out on the differences at final visit to baseline. In case the normality assumption is not verified, the corresponding non parametric test will be adopted (Table E.4b2). These data will also be listed (Appendix 3: Listing E.3).

### 7.2.5 Intention To Use Questionnaire (ITUQ)

Intention To Use Questionnaire (ITUQ) will be presented as frequency table of the scores for each question included in the questionnaire. Each table will compare, for each visit in which the questionnaire was administered, the Hnb group and the EC group frequency of answers (Table E.4c1).

The t-test will be carried out on the differences at final visit to baseline. In case the normality assumption is not verified, the corresponding non parametric test will be adopted (Table E.4c2). These data will also be listed (Appendix 3: Listing E.4).

### 7.2.6 Risk Perception (PRI-P CC)

Risk Perception (PRI-P CC) Questionnaire will be presented as frequency table of the scores for each question included in the questionnaire. Each table will compare, for each visit in which the questionnaire was administered, the Hnb group and the EC group frequency of answers (Table E.4d1).

	e-CIG VS. IQOS Statistical Analysis Plan Version 2.0	Doc code: BIOSTAT.SAP.02
		Pag. 15 of 115

The t-test will be carried out on the differences at final visit to baseline. In case the normality assumption is not verified, the corresponding non parametric test will be adopted (Table E.4d2). These data will also be listed (Appendix 3: Listing E.5).

### **7.2.7 Risk Perception (PRI-P RRP)**

Risk Perception (PRI-P RRP) Questionnaire will be presented as frequency table of the scores for each question included in the questionnaire. Each table will compare, for each visit in which the questionnaire was administered, the Hnb group and the EC group frequency of answers (Table E.4e1)

The t-test will be carried out on the differences at final visit to baseline. In case the normality assumption is not verified, the corresponding non parametric test will be adopted Table E.4e2). These data will also be listed (Appendix 3: Listing E.6).

### **7.2.8 Device Delivery**

Device delivery will be summarized with frequency table for each group. The results will be included in Table E.4f. These data will also be listed (Appendix 3: Listing D.9).

## **7.3 Biomarker of Biological Exposure**

Exhaled breath Carbon monoxide (eCO) will be summarized by timepoint using descriptive summaries as described in Section 5. The parameter will be measured across all the study visits.

Changes from the Baseline Visit to all the subsequent study visits will be also generated. Table E.5 will include the summaries of the data by group. The t-test will be carried out on the changes from baseline to last visit. In case the normality assumption is not verified, the corresponding non parametric test will be adopted.

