### **Minimum Glossary**

**Efficacy:** the quit rate derived from the use of the product (HnB or EC)

**Adoption rate:** the daily product use (HnB or EC), measured independently from tobacco cigarette consumption

**Tolerability:** the incidence of adverse or serious adverse events derived from the use of the product (HnB or EC)

**Tobacco harm reduction:** reduction of selected biomarkers of exposure in spot urine and improvement in some biological parameters.

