#### **Secondary study endpoints:**

Different urinary metabolites will be evaluated at week 4 by means of a descriptive analysis using 95% confidence intervals, adjusted for confounding variables and for the baseline log-transformed level of the biomarker.

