## 1 INTRODUCTION

This Statistical Analysis Plan (SAP) is based on the study Protocol Final Version (dated September 26, 2017). The main objective of this document is to provide guidance for the production of the analyses of all the variables included in the Database of the study which will be frozen when the last data is validated in accordance with the Fullcro's SOPs.

This document will also provide guidance for the production of the Statistical Report (SR), the in-text tables, the in-text listings and the Tables/Figures/Listings (TFLs) which will be part of the SR as Appendices (they will regard the data of all patients and all variables included in the Database).

The Statistical analysis will begin once the data validation is complete and will proceed according to this plan. In case of deviations from this SAP, explanations in the Statistical Report (SR) will be provided.

This document refers to the analysis of all the variables included in the Clinical Data Base.

All details on the decisions made during the Data Review Meeting (DRM) will be described in an *ad hoc* section in Version 2.0 of the present document that will be produced before the Database freezing.

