### 2.2 Study Objectives

The primary objective of this study is to compare the efficacy of HnB and EC, in terms of quit rates at week 12, by self-reporting abstinence from classic cigarette [validated by an Exhaled breath Carbon monoxide (eCO) measurement  $\leq 10$ ppm].

The secondary objectives are:

- 1) to compare the smoking reduction derived from the use of HnB and EC, intended as a 50% reduction in the number of conventional cigarette/day at week 12, defined through self-reporting;
- 2) to compare the adoption rate, and adherence to product use [by collecting (empty) refill bottles and used heatsticks on a daily basis, verified by a study diary filled daily by the subject];
- 3) to compare the acceptability of HnB and of EC, through the assessment of product satisfaction, risk perception, effects on craving and nicotine withdrawal, product preferences, subjective and sensorial effects by:
  - a) Modified Cigarette Evaluation Questionnaire (mCEQ) adapted for EC and HnB users;
  - b) three of 8 items of "Smoking Cue Appeal" adapted for EC and HnBusers;
  - c) "Intent to use questionnaire" (ITUQ) – items 4-6;
  - d) PRI-P CC Perceived Health Risk scale (for classic cigarette)
  - e) PRI-P RRP Perceived Health Risk scale (for reduced risk products)
  - f) percentage of choice of a particular subtype of heatstick (HnB) or e-liquid.
- 4) to compare the tolerability of HnB and EC, in terms of: self-reported adverse and serious adverse events by study participants, vital signs (BP, HR and body weight) measurements.
- 5) to compare the tobacco harm reduction between HnB and EC, in terms of:
  - a) changes in Biomarkers of Biological Effects (BoBE) such as: eCO in the exhaled breath (i.e. eCO), step test values;

	
e-CIG VS. IQOS Statistical Analysis Plan Version 2.0
	Doc code: BIOSTAT.SAP.02
		Pag. 8 of 115

b) measurement of 14 selected Biomarkers of Exposure (BoE) in spot urine samples of study participants:

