1 tobacco-specific nitrosamine, total NNAL (NNK); 8 volatile organic toxicants (derivates of mercapturic acid, MA): 2-hydroxyethylmercapturic acid (HEMA) also known as ethylene oxide, 2-hydroxy-3-butenyl- mercapturic acid and isomers (MHBMA) also known as 1,3-butadiene, 3-hydroxy-1-methyl propyl- mercapturic acid (HMPMA) also known as crotonaldehyde, 3-hydroxypropylmercapturic acid (3-HPMA) also known as acrolein, S-phenylmercapturic acid (S-PMA) also known as benzene, 2-carbamoylethylmercapturic acid (acrylamide mercapturic acid (AAMA) also known as acrylamide (AAMA and GAMA), 2-cyanoethylmercapturic acid (CEMA) also known as acrylonitrile, 2-hydroxypropylmercapturic acid (2-HPMA) also known as propylene oxide; 4 polycyclic aromatic hydrocarbons: naphthalene, fluorine, phenanthrene, pyrene (1-OHP); cotinine; creatinine.

c) self-perception of "Tobacco Harm Reduction process" through changes in quality of life scores (EQ-5Dquestionnaire);

6) to compare the reliability of HnB and EC, in terms of incidence and kind of malfunctioning events, through self-reporting.

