### **5.2 Derived datasets**

At the moment of the preparation of the present SAP, three derived dataset is forecasted to be created, i.e. the one containing the MedDRA codes for the Adverse Events, the one containing the information about the adherence to the device and the one containing the analysis populations, that will be prepared after the database freezing. In case additional derived dataset will be needed during the analysis phase, details will be provided in the Statistical Report.

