## 7.2 Analysis of secondary endpoints

	e-CIG VS. IQOS Statistical Analysis Plan Version 2.0	Doc code: BIOSTAT.SAP.02
		Pag. 13 of 115

The secondary endpoints refer to the smoking reduction, the compliance to the study product and the acceptability of HnB or EC. The analyses to be performed on the smoking reduction and the adoption rate will be presented in sections 7.2.1 and 7.2.2 respectively. As for the latter, the endpoint will be analyzed through the product satisfaction, the risk perception, the effects on craving and nicotine withdrawal, the product preferences, the subjective and sensorial effects and presented in the sections from 7.2.3 to 7.2.8. In sections 7.3 and 7.4 the results of the analyses on the EQ-5D and the step test by visit will be presented.

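### The SAP keeps the comparison of 14 urinary biomarkers as an objective but specifies no analysis, table or listing of their levels

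*SAP*

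**What the plan says.** **Urinary biomarkers, protocol.** The Minimum Glossary defines tobacco harm reduction as "reduction of selected biomarkers of exposure in spot urine and improvement in some biological parameters". The secondary endpoints compare the two arms on it, and urine is taken at baseline and week 4 and assayed by an external laboratory. The statistics section sets the method: "Different urinary metabolites will be evaluated at week 4 by means of a descriptive analysis using 95% confidence intervals", with adjustment for confounders and for the log of each biomarker's baseline level. The confounders are not named.

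**Urinary biomarkers, SAP.** Section 2.2 repeats the between-arm objective, including "measurement of 14 selected Biomarkers of Exposure (BoE) in spot urine samples of study participants", and its analyte list ends with "naphthalene, fluorine, phenanthrene, pyrene (1-OHP); cotinine; creatinine". Section 7.2 opens its account of the secondary analyses with "The secondary endpoints refer to the smoking reduction, the compliance to the study product and the acceptability of HnB or EC". Section 7.3 begins "Exhaled breath Carbon monoxide (eCO) will be summarized by timepoint using descriptive summaries as described in Section 5" and deals with nothing else. On scope, the Introduction says: "This document refers to the analysis of all the variables included in the Clinical Data Base".

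**Tests on neighbouring endpoints.** Section 7.3 compares the arms on change in eCO from baseline to the last visit by t-test, with a non-parametric test if normality fails. Section 7.4 does the same for EQ-5D at the final visit and sends the result to Table E.4a2. Section 7.5 promises inference on step-test changes by item without naming a test. Mock Table E.7b covers VO2MAX only and names the t-test in a footnote.

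**The concern.** An objective that compares two arms needs an analysis that does so. Here the protocol supplies the outline of one, the SAP restates the objective, and the analysis then drops out. The urinary biomarkers are half of the protocol's own definition of harm reduction, and a comparison of harm-reduction values between the products is one of the three publication topics in the protocol's dissemination plan.

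The SAP is also where the open details should have been settled: which confounders enter the model, the scale of the outcome, what is done with creatinine, and which population is analysed. The trial is open-label, so these choices are better written down before anyone sees laboratory results by arm.

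**Working it through.** **1. The stated count of 14.** From the analyte list in SAP 2.2: 1 nitrosamine (total NNAL) + 8 mercapturic acids + 4 polycyclic aromatic hydrocarbons + cotinine = 14. This agrees with the documents. Creatinine is a fifteenth listed analyte.

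**2. Search of the SAP for an output of levels.**

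| Place in the SAP | What it holds on urinary biomarkers |
|---|---|
| Index | No section |
| 2.2 | Objective and analyte list |
| 6.6, Table D.6, Listing D.6 | Instructions, containers delivered, urine returned |
| 7.2 overview | Not named |
| 7.3, Table E.5 | eCO only |
| 7.4 and 7.5 | EQ-5D and step test only |
| Appendix 1 | No table or listing of levels |
| Mock tables and listings | None of levels |

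The mock outputs were checked as well because Appendix 1 is not a perfect inventory: it omits Table E.4c1, which 7.2.5 calls for. The result is the same, 0 of 14 biomarkers with an output. The index and Appendix 1 are both in the public copy, so removed pages do not explain the gap.

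**3. Do the general rules in SAP 5 fill it?** They provide n, missing, mean, SD, percentiles, counts and percentages by group. The protocol's analysis also needs confidence intervals, adjustment for confounders and adjustment for log baseline. None of the three is in Section 5.

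**4. Change score against ANCOVA for eCO, EQ VAS and VO2MAX.** Let σ0 and σ1 be the baseline and follow-up SDs and ρ their correlation. Per subject:

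- change score: σ0² + σ1² − 2ρσ0σ1
- ANCOVA on baseline: σ1²(1 − ρ²)
- difference: (σ0 − ρσ1)², which is never negative

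With equal SDs, in units of σ², these become 2(1 − ρ) and 1 − ρ², so the ratio is (1 + ρ)/2. The documents give no ρ, so a range is shown.

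| Assumed ρ | Change score | ANCOVA | Ratio | Extra subjects a change score needs |
|---|---|---|---|---|
| 0.2 | 1.60 | 0.96 | 0.60 | 67% |
| 0.5 | 1.00 | 0.75 | 0.75 | 33% |
| 0.7 | 0.60 | 0.51 | 0.85 | 18% |
| 0.9 | 0.20 | 0.19 | 0.95 | 5% |

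The last column is 1/ratio − 1. The comparison is with the t-test and does not carry over to the non-parametric fallback.

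**5. Test visit.** The text says last visit for eCO, final visit for EQ-5D and nothing for the step test. Week 12 (V6) and week 24 (V7) are both possible. Free product supply stops at V6, so the two visits measure different conditions.

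**6. Cross-reference.** Table E.4a2, to which 7.4 sends the EQ-5D test, is the mCEQ table. The EQ-5D table, E.6, has no p-value.

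**The case against.** The strongest defence is scope. The SAP confines itself to the clinical database and the assays come from an outside laboratory, so the results may have been meant for a separate analysis. That is possible, and a citation of such a plan would answer the point. But the SAP keeps the objective and nowhere says that the results are excluded or handled elsewhere. It does flag other gaps, for example that the protocol left the analysis populations undefined.

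Some of the evidence is weaker than it looks, and this part of the objection stands:

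- Section 7.3 is not wrong about eCO. The protocol classes eCO as a biomarker of biological effect, separate from the urinary biomarkers of exposure. What is missing is a section for the latter.
- The overview in 7.2 does not name eCO either, yet eCO is analysed. Its silence proves little alone.
- Section 5.2 says "three derived dataset is forecasted to be created", none of them for laboratory results. Assay values would be source data rather than a derived dataset, and 5.2 allows further datasets to be added.

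The omission rests on the full search of sections, lists and mock outputs, not on any one of these.

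On the neighbouring endpoints, change-score tests are consistent with the protocol's general wording on between-group tests, and equal SDs are doubtful for eCO when some participants switch fully and others do not. Both remarks are fair. Unequal SDs alter the size of the gain but not its direction, since the difference in step 4 is a square.

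**Conclusion.** The point holds for the urinary biomarkers. Followed as written, the SAP leaves a stated between-arm objective without any analysis, table or listing, although the protocol outlines one. The size is 0 of 14 biomarkers covered. This finding is a matter of record and rests on no numerical assumption. The primary endpoint is not touched.

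The ANCOVA point is an improvement, not an error. Its size depends on ρ and, for the simple ratio, on equal SDs: a variance ratio of 0.60 to 0.95 for ρ from 0.2 to 0.9.

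Three stronger readings are tempting and not supported:

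- A reader might infer that the whole biomarker analysis is left to be chosen after the data are in. The protocol already fixes the time point, the confidence intervals and the log-baseline covariate. What is open is the naming of confounders and the details of model and presentation.
- A reader might infer that the biomarkers will never be analysed. The documents show only that this SAP neither analyses them nor says where they are analysed.
- A reader might infer from the mock tables that eCO, EQ-5D and VO2MAX are tested at V7. Only the descriptive change column of Table E.7a names Visit 7. The p-value in E.5 and the test in E.7b carry no visit, and the SAP also uses final visit for the week-12 primary comparison (Table E.1b). The test visit is undefined, no more than that.

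**What to change.** **Main change.** Add a SAP section, a table and a listing for the 14 biomarkers that carry out the protocol's analysis: week-4 level by arm with 95% confidence interval, adjusted for log baseline and for named baseline confounders. State how the external laboratory results enter the analysis database. If another plan covers them, cite it instead. A log-scale outcome, creatinine correction and an HnB/EC geometric mean ratio are recommended options; the protocol does not require them.

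**Low-cost improvement.** For eCO, EQ VAS and VO2MAX, replace the unadjusted change-score t-test with ANCOVA adjusted for the baseline value.

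**Clarifications.** Name the visit (V6 or V7) at which these endpoints are tested, and make text and mock tables agree. Correct the EQ-5D reference to Table E.4a2 in 7.4.

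**Cost.** SAP text and programming, and possibly a data transfer from the laboratory. No new visits, samples or assessments are needed. ANCOVA uses baseline values already collected and adds a little modelling. The main change should be made before laboratory results are seen by arm.

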**Tobacco Harm Reduction assessment:**

a) we will record changes in Biomarkers of Biological Effects (BoBE) such as: eCO in the exhaled breath (i.e. eCO) will be assessed at each study visit (+ follow-up at wk 24); step test values at baseline, wk 4, wk 12 (+ follow-up at wk 24).

b) measurement of 14 selected Biomarkers of Exposure (BoE) in spot urine samples of study participants, at baseline (V1) and wk 4 (V4):

tobacco-specific nitrosamine, total NNAL (NNK); 8 volatile organic toxicants (derivates of mercapturic acid, MA): 2-hydroxyethylmercapturic acid (HEMA) also known as ethylene oxide, 2-hydroxy-3-butenylmercapturic acid and isomers (MHBMA) also known as 1,3-butadiene, 3-hydroxy-1-methyl propylmercapturic acid (HMPMA) also known as crotonaldehyde, 3-hydroxypropylmercapturic acid (3-HPMA) also known as acrolein, S-phenylmercapturic acid (S-PMA) also known as benzene, 2-carbamoylethylmercapturic acid (acrylamide mercapturic acid (AAMA) also known as acrylamide (AAMA and GAMA), 2-cyanoethylmercapturic acid (CEMA) also known as acrylonitrile, 2-hydroxypropylmercapturic acid (2-HPMA) also known as propylene oxide; 4 polycyclic aromatic hydrocarbons: naphthalene, fluorine, phenanthrene, pyrene (1-OHP); cotinine; creatinine.

**Lab analysis:** urine samples will be collected at baseline and wk 4, and sent to an external laboratory to search for any modifications in the above mentioned Biomarkers of Exposure (BoE); the lab selected is ABF GmbH: SOPs for urine collection and lab procedures are available and briefly described in the quotation attached.

c) Self-perception of “Tobacco Harm Reduction process” will be assessed by changes in quality of life score at baseline, wk 4, wk 8, wk 12 (+ follow-up at wk 24). The quality of life will be assessed by a validated visual analogic scale specifically designed to measure this topic and named “EQ-5D”;

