## **7.4 EQ-5D**

The Euro Quality of Life Questionnaire (EQ-5D) will be presented as descriptive summary table by visit. Acceptability of HnB and of EC will be analyzed through the assessment of several questionnaires. The analyses will be presented through the five dimensions (i.e. Mobility, Self-Care, Usual Activities, Pain/Discomfort, Anxiety/Depression) and a Visual Analogue Scale (EQ VAS). Changes from the Baseline Visit to all the subsequent study visits will be also generated. The results will be included in Table E.6 (Appendix 2).

The t-test will be carried out on the differences at final visit to baseline. In case the normality assumption is not verified, the corresponding non parametric test will be adopted. The results will be

	e-CIG VS. IQOS Statistical Analysis Plan Version 2.0	Doc code: BIOSTAT.SAP.02
		Pag. 16 of 115

included in Table E.4a2 (Appendix 2). These data will also be listed (Appendix 3: Listing E.1). The analysis will be presented by all subjects and “Continuous Quitters”.

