### 7.5 Step test by visit

The Step test data will be presented as descriptive summary table by visit. The seven items regarding Heart Rate and Oxygen Saturation (i.e. Baseline, Step 1 to 5 and Baseline condition recovery time) will be analysed by HR and SpO2. The two items, (i.e. Stop time and VO2MAX, will be analysed using the same methods (Table E.7a). In details, the latter, is the result of the so called “Chester Step Test” who was computed for each subject at site and reported in the eCRF.

An inferential analysis will be carried out on the changes from baseline by item. The results will be presented in Table E.7b. The data will also be listed (Appendix 3: Listing D.8). The analysis will be presented by all subjects and “Continuous Quitters”.

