...	Mean	XX.X	XX.X	X.XXXX
Question 8	Mean	XX.X	XX.X	X.XXXX
TOTAL	Mean	XX.X	XX.X	X.XXXX

<File: [..]\Work\_In\_Progress\[..]\Statistica\Programmi\xxxxx.sas>  
<Source: [..]\Work\_In\_Progress\[..]\Gestione Dati\Dati SAS\xxxxx.sas7bdat>      Generated on XXXXXXXXXX XX:XX  
For the inferential analysis, the scores were considered as numbers.  
The p-value was derived from the XXXX test  
For further information see Listing X.X

Sponsor: Center for Tobacco Research, Cessation and Prevention, [name]  
Protocol: Progetto e-cig vs IQOS

Table E.4c1 Summary of the ITU Questionnaire by visit. <Question 4 (of questions 4-5-6)>  
Population: <Per-Protocol/Intention-To-Treat>

<Question>

Visit	Score	Group HnB	Group EC
Visit 4	1	XX (XX.X%)	XX (XX.X)
	2	XX (XX.X%)	XX (XX.X)
	3	XX (XX.X%)	XX (XX.X)
	4	XX (XX.X%)	XX (XX.X)
	5	XX (XX.X%)	XX (XX.X)
	6	XX (XX.X%)	XX (XX.X)
	7	XX (XX.X%)	XX (XX.X)
Visit 5	1	XX (XX.X%)	XX (XX.X)
	2	XX (XX.X%)	XX (XX.X)
	3	XX (XX.X%)	XX (XX.X)
	4	XX (XX.X%)	XX (XX.X)
	5	XX (XX.X%)	XX (XX.X)
	6	XX (XX.X%)	XX (XX.X)
	7	XX (XX.X%)	XX (XX.X)
Visit 6	1	XX (XX.X%)	XX (XX.X)
	2	XX (XX.X%)	XX (XX.X)
	3	XX (XX.X%)	XX (XX.X)
	4	XX (XX.X%)	XX (XX.X)
	5	XX (XX.X%)	XX (XX.X)
	6	XX (XX.X%)	XX (XX.X)
	7	XX (XX.X%)	XX (XX.X)
Visit 7	1	XX (XX.X%)	XX (XX.X)
	2	XX (XX.X%)	XX (XX.X)
	3	XX (XX.X%)	XX (XX.X)
	4	XX (XX.X%)	XX (XX.X)
	5	XX (XX.X%)	XX (XX.X)
	6	XX (XX.X%)	XX (XX.X)
	7	XX (XX.X%)	XX (XX.X)

<File: [..]\Work\_In\_Progress\[..]\Statistica\Programmi\xxxxx.sas>

<Source: [..]\Work\_In\_Progress\[..]\Gestione Dati\Dati SAS\xxxxx.satd7sas> Generated on XXXXXXXX XX:XX

Legend: 1. Assolutamente falso ; 2. Falso ; 3. Piuttosto falso ; 4. Piuttosto vero ; 5. Vero ; 6. Molto vero ; 7. Verissimo

For further information see Listing X.X

Sponsor: Center for Tobacco Research, Cessation and Prevention, [name]  
Protocol: Progetto e-cig vs IQOS

Table E.4c2 ITU Questionnaire. Inferential analysis on the mean changes at final visit from baseline  
Population: <Per-Protocol/Intention-To-Treat>

		Group HnB N=XXXX	Group EC N=XXXX	p-value
Question 4	Mean	XX.X	XX.X	X.XXXX
Question 5	Mean	XX.X	XX.X	X.XXXX
Question 6	Mean	XX.X	XX.X	X.XXXX
TOTAL	Mean	XX.X	XX.X	X.XXXX

Sponsor: Center for Tobacco Research, Cessation and Prevention, [name]  
Protocol: Progetto e-cig vs IQOS

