Self-care (1-5)	Visit 1	XX	XX	XX.X	XX.X	[X.X , X.X]	XX.X	(X - X)							
	Visit 4	XX	XX	XX.X	XX.X	[X.X , X.X]	XX.X	(X - X)							
	Visit 5	XX	XX	XX.X	XX.X	[X.X , X.X]	XX.X	(X - X)							
	Visit 6	XX	XX	XX.X	XX.X	[X.X , X.X]	XX.X	(X - X)							
	Visit 7	XX	XX	XX.X	XX.X	[X.X , X.X]	XX.X	(X - X)	XX	XX	XX.X	XX.X	[X.X , X.X]	XX.X	(X - X)
.....															
Health-today (0-100)	Visit 1	XX	XX	XX.X	XX.X	[X.X , X.X]	XX.X	(X - X)							
	Visit 4	XX	XX	XX.X	XX.X	[X.X , X.X]	XX.X	(X - X)							
	Visit 5	XX	XX	XX.X	XX.X	[X.X , X.X]	XX.X	(X - X)							
	Visit 6	XX	XX	XX.X	XX.X	[X.X , X.X]	XX.X	(X - X)							
	Visit 7	XX	XX	XX.X	XX.X	[X.X , X.X]	XX.X	(X - X)	XX	XX	XX.X	XX.X	[X.X , X.X]	XX.X	(X - X)

<File: [..]\Work\_In\_Progress\[..\]Statistica\Programmi\xxxxx.sas>

<Source: [..]\Work\_In\_Progress\[..\]Gestione Dati\Dati SAS\xxxxx.sas7bdat>

Generated on XXXXXXXX XX:XX

For further information see Listing X.X

e-CIG VS. IQOS  
Statistical Analysis Plan  
Version 2.0

Doc code:  
BIOSTAT.SAP.02

Pag. 60 of 115

Sponsor: Center for Tobacco Research, Cessation and Prevention, [name]  
Protocol: Progetto e-cig vs IQOS

Table E.7a Summary of Step Test by group < Group HnB / Group EC >  
Population: <Per-Protocol/Intention-To-Treat>

Parameter	Visit	Observed Values at Visit						Changes From Visit 1 to Visit 7							
		N	N miss	Mean	STD	CI 95%	Median	Range (Q1-Q3)	N	N miss	Mean	STD	CI 95%	Median	Range (Q1-Q3)
Baseline HR	Visit 1	XX	XX	XX.XX	XX.XX	[XX.XX,XXX.X]	XX.XX	(XX.XX - XXX.X)							
	Visit 4	XX	XX	XX.XX	XX.XX	[XX.XX,XXX.X]	XX.XX	(XX.XX - XXX.X)							
	Visit 6	XX	XX	XX.XX	XX.XX	[XX.XX,XXX.X]	XX.XX	(XX.XX - XXX.X)							
	Visit 7	XX	XX	XX.XX	XX.XX	[XX.XX,XXX.X]	XX.XX	(XX.XX - XXX.X)	XX	XX	XX.XX	XX.XX	[XX.XX,XXX.X]	XX.XX	(XX.XX - XXX.X)
SpO2	Visit 1	XX	XX	XX.XX	XX.XX	[XX.XX,XXX.X]	XX.XX	(XX.XX - XXX.X)							
	Visit 4	XX	XX	XX.XX	XX.XX	[XX.XX,XXX.X]	XX.XX	(XX.XX - XXX.X)							
	Visit 6	XX	XX	XX.XX	XX.XX	[XX.XX,XXX.X]	XX.XX	(XX.XX - XXX.X)							
	Visit 7	XX	XX	XX.XX	XX.XX	[XX.XX,XXX.X]	XX.XX	(XX.XX - XXX.X)	XX	XX	XX.XX	XX.XX	[XX.XX,XXX.X]	XX.XX	(XX.XX - XXX.X)
Step 1 HR	Visit 1	XX	XX	XX.XX	XX.XX	[XX.XX,XXX.X]	XX.XX	(XX.XX - XXX.X)							
	Visit 4	XX	XX	XX.XX	XX.XX	[XX.XX,XXX.X]	XX.XX	(XX.XX - XXX.X)							
	Visit 6	XX	XX	XX.XX	XX.XX	[XX.XX,XXX.X]	XX.XX	(XX.XX - XXX.X)							
	Visit 7	XX	XX	XX.XX	XX.XX	[XX.XX,XXX.X]	XX.XX	(XX.XX - XXX.X)	XX	XX	XX.XX	XX.XX	[XX.XX,XXX.X]	XX.XX	(XX.XX - XXX.X)

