SpO2	Visit 1	XX	XX	XX.XX	XX.XX	[XX.XX,XXX.X]	XX.XX	(XX.XX - XXX.X)							
	Visit 4	XX	XX	XX.XX	XX.XX	[XX.XX,XXX.X]	XX.XX	(XX.XX - XXX.X)							
	Visit 6	XX	XX	XX.XX	XX.XX	[XX.XX,XXX.X]	XX.XX	(XX.XX - XXX.X)							
	Visit 7	XX	XX	XX.XX	XX.XX	[XX.XX,XXX.X]	XX.XX	(XX.XX - XXX.X)	XX	XX	XX.XX	XX.XX	[XX.XX,XXX.X]	XX.XX	(XX.XX - XXX.X)
...															
Recovery HR	Visit 1	XX	XX	XX.XX	XX.XX	[XX.XX,XXX.X]	XX.XX	(XX.XX - XXX.X)							
	Visit 4	XX	XX	XX.XX	XX.XX	[XX.XX,XXX.X]	XX.XX	(XX.XX - XXX.X)							
	Visit 6	XX	XX	XX.XX	XX.XX	[XX.XX,XXX.X]	XX.XX	(XX.XX - XXX.X)							
	Visit 7	XX	XX	XX.XX	XX.XX	[XX.XX,XXX.X]	XX.XX	(XX.XX - XXX.X)	XX	XX	XX.XX	XX.XX	[XX.XX,XXX.X]	XX.XX	(XX.XX - XXX.X)
SpO2	Visit 1	XX	XX	XX.XX	XX.XX	[XX.XX,XXX.X]	XX.XX	(XX.XX - XXX.X)							
	Visit 4	XX	XX	XX.XX	XX.XX	[XX.XX,XXX.X]	XX.XX	(XX.XX - XXX.X)							
	Visit 6	XX	XX	XX.XX	XX.XX	[XX.XX,XXX.X]	XX.XX	(XX.XX - XXX.X)							
	Visit 7	XX	XX	XX.XX	XX.XX	[XX.XX,XXX.X]	XX.XX	(XX.XX - XXX.X)	XX	XX	XX.XX	XX.XX	[XX.XX,XXX.X]	XX.XX	(XX.XX - XXX.X)

<File: [..]\Work\_In\_Progress\[..]\Statistica\Programmi\xxxxx.sas>  
 <Source: [..]\Work\_In\_Progress\[..]\Gestione Dati\Dati SAS\xxxxx.satd7sas> Generated on XXXXXXXX XX:XX  
 The percentages are calculated on the total of the enrolled patients by group  
 For further information see Listing X.X

Sponsor: Center for Tobacco Research, Cessation and Prevention, [name]  
Protocol: Progetto e-cig vs IQOS

Table E.7b Summary of Step Test - inferential analysis of VO2MAX  
Population: <Per-Protocol/Intention-To-Treat>

		Group HnB	Group EC
VO2MAX	N	XX	XX
	N missing	XX	XX
	Mean	XX.X	XX.X
	Std. deviation	XX.X	XX.X
	Median	XX.X	XX.X
	Q1-Q3	X.X - XX.X	X.X - XX.X
p-value=X.XXXX			

---

<File: [..]\Work\_In\_Progress\[..]\Statistica\Programmi\xxxxx.sas>  
<Source: [..]\Work\_In\_Progress\[..]\Gestione Dati\Dati SAS\xxxxx.satd7sas> Generated on XXXXXXXX XX:XX  
The p-values was derived from the t-test  
For further information see Listing X

	e-CIG VS. IQOS Statistical Analysis Plan Version 2.0	Doc code: BIOSTAT.SAP.02
		Pag. 62 of 115

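### eCO, EQ-5D and step-test comparisons rest on raw change to an unnamed visit, with an incompletely specified test and no adjustment for the V1 value

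*SAP*

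**What the plan says.** **eCO (SAP 7.3).** "The t-test will be carried out on the changes from baseline to last visit". Then: "In case the normality assumption is not verified, the corresponding non parametric test will be adopted". Table E.5 gives each arm's means and changes with within-arm intervals, plus one p-value.

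**EQ-5D (SAP 7.4).** "The t-test will be carried out on the differences at final visit to baseline", with the same switching sentence. The inferential results are sent to Table E.4a2, but that shell lists only mCEQ domains. Table E.6 is descriptive, by arm.

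**Step test (SAP 7.5).** "An inferential analysis will be carried out on the changes from baseline by item". The text names no test, no normality switch and no visit. Table E.7b covers VO2MAX only and carries the footnote "The p-values was derived from the t-test".

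**Visit.** The text of 7.3 and 7.4 plans descriptive changes to every later visit. In the shells of Tables E.5, E.6 and E.7a, the change cells are filled only in the follow-up (V7) row, and E.7a is headed "Changes From Visit 1 to Visit 7".

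**Baseline.** All three measures have a V1 value in the protocol's visit schedule. For eCO, the protocol says it "will be assessed at each study visit (+ follow-up at wk 24"). The protocol's statistics section adjusts the urinary biomarkers, which belong to the same harm-reduction objective, for their log-transformed baseline level. No such adjustment is planned for eCO, EQ-5D or the step test.

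**The concern.** Three things are left open that a plan should close.

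- **The test.** For eCO and EQ-5D, the data that supply the p-value first decide which test supplies it, by an unstated criterion. A t-test compares means and a rank test does not, so the quantity being compared is also undecided. Questionnaire shells under the same rule, such as Table E.4b2, still carry a placeholder: "The p-value was derived from the XXXX test".
- **The visit.** Free supply of the products ends at V6 (week 12), and V7 falls 12 weeks later. The protocol states the ban on other tobacco products for the 12-week study. A comparison at V7 therefore answers a different question from one at V6.
- **The estimate.** A change score uses the baseline by subtraction, which fixes its coefficient at 1. ANCOVA estimates that coefficient and is at least as precise in large samples. Tables E.5 and E.7b give a p-value but no between-arm difference with an interval, so a non-significant result would not show how similar the products are.

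At stake is how clearly and precisely these secondary harm-reduction comparisons can be read.

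**Working it through.** **The plan's own figure.** The only sample size in the documents is 104 per group for the binary primary endpoint (Farrington-Manning, one-sided alpha 0.05, power 0.80, margin 0.15, both rates 0.25). With constrained rates of 0.189 and 0.339, n = [(1.645 × 0.614 + 0.842 × 0.612)/0.15]² = 103.5 (evaluated unrounded), so 104. It reproduces, but has no bearing here: no SD, correlation or power is stated for a continuous endpoint.

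**Inputs.** ITT is 217 (SAP 9.7). The split by arm is not given, so about 108 per arm is assumed. A two-sided 0.05 level is also assumed. The correlation r between baseline and follow-up is not in the documents, so a range is shown.

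**Precision.** Per-patient variances, with SD_b at baseline and SD_f at follow-up:

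- Change score: SD_b² + SD_f² − 2r·SD_b·SD_f
- ANCOVA: SD_f²(1 − r²)
- Excess of the first over the second: (SD_b − r·SD_f)², which is never negative and is zero only when SD_b = r·SD_f

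With equal SDs the ratio is (1 − r²)/[2(1 − r)] = (1 + r)/2. The detectable difference at 80% power is (1.96 + 0.842) × √(2/108), times √[2(1 − r)] for the change score or √(1 − r²) for ANCOVA.

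| r | Variance ratio | Interval width | ANCOVA power where change score has 80% | Detectable difference, change score to ANCOVA (outcome SDs) |
|---|---|---|---|---|
| 0.3 | 0.65 | −19.4% | 93.5% | 0.451 to 0.364 |
| 0.5 | 0.75 | −13.4% | 89.9% | 0.381 to 0.330 |
| 0.7 | 0.85 | −7.8% | 86.0% | 0.295 to 0.272 |
| 0.9 | 0.95 | −2.5% | 82.0% | 0.170 to 0.166 |

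**The switching rule.** The SAP names neither the check nor the alternative, so the simulation assumed Shapiro-Wilk at 0.05 on residuals, then a t-test or Mann-Whitney test. It used 108 per arm and 6,000 null trials per scenario (Monte Carlo SE about 0.003).

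| Distribution of changes | Switched to rank test | Type I error of the rule | t-test and rank test disagree on significance |
|---|---|---|---|
| Normal | 4.8% | 0.050 | 2.1% |
| t, 5 df | 83.9% | 0.049 | 2.7% |
| Lognormal | 100% | 0.054 | 4.1% |
| Quitter/non-quitter mixture | 64.1% | 0.053 | 1.3% |

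The error rate holds. What remains uncertain in advance is which test, and so which comparison, would be reported.

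**The visit.** The SAP's usage is inconsistent. Table E.1b calls the primary comparison a final-visit one, and SAP 7.1 sets that endpoint at week 12. Table S.1 counts exposure to Visit 6. The change cells in E.5 to E.7a point to V7. The choice has consequences. Per-Protocol is 193 and Per-Protocol V7 is 177, so 193 − 177 = 16 subjects completed the visits to V6 but are not in the V7 set. If the tested visit is V7, then under LOCF (SAP 5.1 and section 2.4 of the data review minute) week-12 values would stand in for missing week-24 values.

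**The case against.** The strongest reply is that nothing here is invalid. Under randomisation a change score gives an unbiased comparison, the protocol words these objectives as changes, SAP 5 calls the analysis descriptive, and the simulation shows the error rate holds. That all stands. The gain from ANCOVA is one of efficiency.

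The size of the gain is also not in the documents. It is small at high r, and equal SDs are doubtful for eCO, where stopping smoking may alter the spread. This stands too. Only the direction, that the gain cannot be negative, is free of those assumptions.

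On the visit, a reader might infer that harm reduction is to be tested only at week 24. The evidence is too thin. It comes from mock cells, and Table S.3 names Visits 6 and 7 in its change heading yet fills only the follow-up row, so the filled cells may be shorthand. The supportable point is that the tested visit is not named.

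Finally, a large-sample argument for comparing means does not reach every planned analysis. EQ-5D and the step test are also analysed in Continuous Quitters. At the planned 20-25% quit rate that is 0.20 × 110 = 22 to 0.25 × 110 = 27.5 per arm, in a subgroup defined after randomisation. Nor does linear ANCOVA suit the five EQ-5D items scored 1 to 5. Both limits are accepted and shape the fix.

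**Conclusion.** The point holds for eCO, EQ-5D and the step test, in differing ways. For eCO and EQ-5D, the test depends on the data through an unnamed check and an unnamed alternative. For the step test there is no switch; the fault is that the text names neither test nor visit, and speaks of tests by item where Table E.7b covers VO2MAX only. In all three, the V1 value is available but not used as a covariate. The missing between-arm interval in Tables E.5 and E.7b does not come from the switch: it is missing under the t-test as well.

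As an illustration, ANCOVA would save 35%, 25%, 15% or 5% of the variance at r = 0.3, 0.5, 0.7 or 0.9, assuming equal SDs. Citing only the low-r end would overstate the case.

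Stronger readings are not supported. The baseline is not ignored, since subtraction uses it. False-positive rates were not inflated. The point does not extend to every continuous endpoint: the SAP only summarises vital signs, the protocol already adjusts the urinary biomarkers, and the acceptability questionnaires are first given at V4, so they have no baseline to adjust for, which is a separate problem. The primary conclusion and sample size are unaffected. The change is worth making because it is cheap and cannot reduce large-sample precision.

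**What to change.** In SAP 7.3 to 7.5:

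1. For eCO, EQ VAS and VO2MAX, delete the normality pre-test where there is one. Specify one ANCOVA of the week-12 (V6) value on arm and the V1 value with robust standard errors, reporting the adjusted HnB-EC difference and 95% interval.
2. Use a log scale for eCO if it is skewed. Fix that choice beforehand, for example from V1 values pooled over arms, with a rule for zero readings. Otherwise one data-driven choice replaces another.
3. Name one rank-based sensitivity analysis, such as a rank ANCOVA.
4. Analyse the five 1-5 EQ-5D items with an ordinal method.
5. Report V7 as follow-up, and treat the Continuous Quitter analyses as descriptive.
6. Add the adjusted difference and interval to Tables E.5 and E.7b, and give EQ-5D its own inferential shell in place of the reference to Table E.4a2.

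Naming V6 stops week-12 values standing in for week 24, but LOCF could still fill V6 for earlier dropouts, so the SAP should state how missing V6 values are handled.

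The cost is a few lines of SAP text, shell edits and a short program, with no new data. If the analysis has already begun, the change belongs in the Statistical Report as an explained deviation, as SAP section 1 provides.
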